6.3.2. Evaluation of Adverse Events or Laboratory Abnormalities

While specific monitoring, diagnostic testing, and supportive care measures must be instituted based on the clinical judgment of the investigator, investigators are encouraged to contact either the PTC Therapeutics medical monitor (or designee) to obtain guidance and to ascertain whether similar events are being seen at other investigator sites. The PTC Therapeutics medical monitor should be notified of any adverse event or laboratory abnormality that leads to dose interruption and should be apprised of ancillary laboratory or other diagnostic findings and the evolving data from any work-up of the initial abnormality. The PTC Therapeutics medical monitor may suggest review of the case with gastroenterology or nephrology consultants or with other experts (either at the site or retained by PTC Therapeutics).

Clinical evaluations for potential hepatic and renal toxicities may include the following:

- **Hepatic:** The medical history, all clinical blood values (particularly serum bilirubin, CK, GGT, AST, and ALT values), and all concomitant medications should be reviewed. Depending upon changes observed, the recommended diagnostic workup may include more

frequent monitoring or further evaluations for viral hepatitis and immune disorders; tests for cholelithiasis; or abdominal ultrasound, computed tomography (CT), magnetic resonance imaging (MRI), or other imaging methods.

- **Renal:** The medical history, baseline ultrasound data, all clinical blood and urine renal values, serum electrolytes, medications, and potential pre- or post renal conditions should be reviewed. Depending upon the changes observed, recommended diagnostic workup may include further evaluations of blood or urine; tests of glomerular filtration rate (GFR), concentrating ability, or other renal functions; CT, MRI, or other imaging methods; and/or renal biopsy.

6.3.3. Instructions for Resuming Study Drug Administration after an Interruption for Safety Concerns

In deciding whether to reinstitute study drug after a dose interruption for any clinically significant safety concern, the investigator should consider factors such as the type and severity of the adverse event or laboratory abnormality, the potential causal relationship of study drug, the patient's status in terms of dystrophinopathy or other health conditions, and the ability to monitor for recurrence of the event.

For hepatic or renal events (refer to [Table 2](#)), the level of investigator certainty that an abnormality leading to drug interruption is drug-related should be considered strongly in deciding whether or not to reinstitute study drug treatment. If the investigator considers the hepatic or renal event to that led to study drug interruption to be probably related to study drug, restarting study drug is not advised. In this case, the patient should be discontinued from the study (see [Sections 6.3.4 and 9](#)). If the investigator considers the hepatic or renal event that prompted study drug interruption to be possibly related or unlikely related to study drug, the investigator should use best judgment in determining whether to restart study drug. If the hepatic or renal event is considered unrelated to study drug, reinstitution of study drug is recommended.

If the investigator believes it is appropriate to do so and the PTC Therapeutics medical monitor has been consulted, study drug may be re-initiated. If the event was determined to be unrelated to study drug, the study drug may be resumed at full dose. Otherwise, if the drug is resumed, it should be reinitiated at half of the original dose. In the event that continuing at a reduced dose is appropriate, the investigator will call the IVR/IWR system, enter the patient number, and inform the IVR/IWR system of the need for dose reduction. The IVR/IWR system will provide details regarding the revised number of study drug sachets to be used per dose. The appropriate clinic staff should instruct the patient/caregiver about the revised number of study drug sachets to be used per dose according to the new schedule provided by the IVR/IWR system.

In general, after dose reduction, the dose should not be returned to the original dose level. However, if further evaluation reveals that the adverse event that led to dose reduction was not related to the study drug, the dose may be escalated to the original dose level. In the event that a return to the original dose level is warranted, the investigator will call the IVR/IWR system, enter the patient number and inform the IVR/IWR system of the need for returning to the original dose. The IVR/IWR system will provide details regarding the revised number of study drug sachets to be used per dose. The appropriate clinic staff should instruct the patient/caregiver

about the revised number of study drug sachets to be used per dose according to the schedule provided by the IVR/TWR system.

If after dose reduction, the patient experiences a recurrence of a previous abnormality that led to study drug dose interruption or experiences the new occurrence of an unacceptable adverse event or laboratory abnormality, the investigator should interrupt study drug and confer with the PTC Therapeutics medical monitor regarding the potential need to discontinue study drug permanently.

6.3.4. Instructions for Discontinuation of Study Drug Administration for Safety Concerns

If after appropriate consideration of study drug interruption/modification and consultation with the PTC Therapeutics medical monitor, it is not appropriate for a patient to continue with study treatment, then study drug should be permanently discontinued. After permanent discontinuation of study drug for a safety concern, and if the initial event was reported as a SAE, then a follow-up SAE report form should be completed. In the case of a treatment discontinuation due to an event that is not an SAE, the PTC Therapeutics medical monitor should be notified (see [Section 9](#)). In addition, details regarding the reasons for discontinuation and the adverse events leading to the discontinuation should be recorded in the source documents and in the appropriate CRF. The End of Treatment Visit CRF should be completed and appropriate follow-up (at ~6 weeks as per protocol or until recovery from or stabilization of the adverse event, whichever comes last) should be instituted.

6.4. Concomitant and Supportive Therapy

Other than the study drug, any treatments (including prescription and non-prescription drugs, health foods, herbal remedies, self-prescribed drugs, street drugs, tobacco products, or alcohol) that are taken by a patient during the screening period, during study drug administration, and for 6 weeks after discontinuation of study drug are considered concomitant medications. Information regarding any concomitant medications will be collected and documented in the concomitant medication CRF page and in the source documents by the clinic staff.

6.4.1. Corticosteroids

To date, corticosteroids use is the only pharmacological intervention that has demonstrated benefit in DMD [[Mendell 1989](#), [Fenichel 1991a](#), [Fenichel 1991b](#), [Griggs 1991](#), [Biggar 2001](#), [Beenakker 2005a](#), [Biggar 2006](#), [Pradhan 2006](#)]. To minimize potential confounding effects of changes in corticosteroid therapy on the interpretation of study results, the use of these medications must be standardized as much as possible during the study.

A stable and standardized corticosteroid regimen should be maintained during the 144 weeks of study drug treatment. Adjustments in corticosteroid dosage for increases in body weight are permitted but are not mandatory. Upward adjustments in corticosteroid dose for increases in body weight or other reasons should follow recommendations provided in Appendix A.

If a patient experiences a concerning corticosteroid-related adverse event (eg. hypertension), interventions or potential adjustments in the corticosteroid dosage may be considered, as detailed in Appendix A. It should be emphasized that reductions in corticosteroid dosage for cosmetic or

other minor reasons should be avoided. Patients who require corticosteroid interruption, dose modification, or reinstatement may remain on study drug therapy.

6.4.2. Aminoglycosides

Renal abnormalities were observed in an international, multicenter, double-blind, placebo-controlled Phase 3 trial evaluating ataluren in patients ≥ 6 years of age with nonsense mutation cystic fibrosis in patients receiving concomitant ataluren and intravenous (IV) aminoglycosides (as described in the Ataluren Investigator Brochure). In patients who require treatment for serious infections, investigators should substitute other antibiotics for systemic aminoglycosides when clinically appropriate. If IV aminoglycosides or other nephrotoxic antibiotics (eg, vancomycin) are administered, study drug must be interrupted during the course of these antibiotics. Patients requiring IV aminoglycoside or vancomycin therapy should be closely monitored in an appropriate setting, such as a hospital. In patients receiving potentially nephrotoxic agents such as IV aminoglycosides or vancomycin, antibiotic drug levels and serum creatinine and BUN should be followed closely. The antibiotic trough level and creatinine and BUN should be measured within 24 to 48 hours of administration of the first antibiotic dose, and further antibiotic dosing should be based on these results. Trough levels should be measured at intervals during the course of antibiotic treatment. Creatinine and BUN should be measured prior to initiating IV aminoglycoside or vancomycin therapy and at least twice a week during the course of antibiotic treatment.

6.4.3. Hydration

Because of the potential risk of renal dysfunction during periods of dehydration in patients receiving study drug, it is important to encourage study patients to maintain adequate hydration throughout the study. Patients should be adequately hydrated prior to receiving potentially nephrotoxic agents such as aminoglycosides or vancomycin, and hydration status should be carefully monitored throughout the administration of these agents. Investigators should be particularly vigilant with patients who are experiencing nausea, vomiting, diarrhea, or fever, or who have laboratory evidence of dehydration.

6.4.4. Cardiac Drugs for CHF Prophylaxis/Treatment

Cardiac drugs (eg, ACE inhibitors, ARBs, beta-blockers, etc) may be used in the treatment of CHF in nonambulatory adolescents with DMD/BMD and may increasingly be considered for use as prophylaxis against symptomatic cardiac dysfunction in younger boys with the disease [Bosser 2004, American Academy of Pediatrics 2005, Duboc 2005, Kajimoto 2006, Ramaciotti 2006]. In addition, recent studies of losartan in the *mdx* mouse model of DMD have suggested salutary effects on skeletal muscle regeneration [Cohn 2007], prompting use of losartan with the hope of disease palliation.

For patients who are on cardiac drugs, a stable regimen should be maintained during the 144 study drug treatment period. Adjustments in dosage or type of drug are permitted to avoid symptoms (eg, cough associated with ACE inhibitors) but attempts should be made to avoid entirely removing patients from CHF prophylaxis/treatment. Patients who require initiation, interruption, dose modification, or reinstatement of CHF prophylaxis/treatment may remain on study drug therapy.

6.4.5. Drugs Metabolized by Cytochrome P450 Enzymes

As the primary route of ataluren metabolism is via glucuronidation by UGT1A9, clinically significant interactions between ataluren and co-administered drugs metabolized by cytochrome P450 enzymes (CYPs) are unlikely. In particular, ataluren is not an inhibitor of CYP1A2, CYP2B6, CYP2C8, CYP2C9, CYP2C19, CYP2D6, and CYP3A4/5, and does not have induction potential on the major CYP enzymes. Based on in vitro studies, ataluren is also not expected to be an inhibitor or a substrate of p-gp mediated transport.

As an added measure of safety, investigators should pay specific attention to use of drugs that are known substrates of this enzyme, particularly when such drugs may have a low therapeutic index.

Drugs that are metabolized by CYP2C8 or CYP2C9 that have low therapeutics indices (in particular, paclitaxel for CYP2C8 and coumarin anticoagulants [eg, warfarin], phenytoin, or tolbutamide for CYP2C9) may be of particular concern. Coumarin anticoagulants are cleared by CYP2C9 and increases in plasma concentrations of coumarin anticoagulants may result in serious clinical consequences. For patients who require anticoagulation during the study, use of an alternative form of anticoagulation (eg, fractionated heparin) should be considered. Phenytoin is metabolized by CYP2C9 and concomitant use with ataluren may be of potential concern. For patients who require anticonvulsant therapy during the study, use of alternative anticonvulsant drugs should be considered.

The metabolism of losartan to its active metabolite may, in part, be mediated by CYP2C9. However, concomitant use of losartan and inhibitors of CYP2C9 have not been examined. Because this drug does not have a narrow therapeutic window, the potential for mild to moderate changes in activity does not require a dose modification.

6.4.6. Potential drug interactions

Based on in vitro studies, ataluren is a substrate of UGT1A9 and breast cancer resistant protein (BCRP). Caution should be exercised when ataluren is co-administered with drugs that are inducers of UGT1A9 (eg, mycophenolate mofetil), or inhibitors of BCRP (eg, cyclosporine).

In vitro data indicate that ataluren is an inhibitor of UGT1A9, organic anion transporter 1 (OAT1), organic anion transporter 3 (OAT3) and organic anion transporting polypeptide 1B3 (OATP1B3). Caution should be exercised when ataluren is co-administered with drugs that are substrates of UGT1A9 (eg, propofol, mycophenolate mofetil), OAT1, OAT3, or OATP1B3 (eg, oseltamivir, acyclovir, ciprofloxacin, captopril, furosemide, bumetanide, valsartan, pravastatin, rosuvastatin, atorvastatin, pitavastatin) because of the risk of increased concentration of these drugs.

6.4.7. Other Concomitant Medications

To the extent possible, administration of any prescription or over-the-counter drug products other than study medication should be minimized during the study period. Patients should be discouraged from use of “health supplements” (eg, creatine, glutamine, coenzyme Q), herbal remedies, growth hormone, self-prescribed drugs, street drugs, tobacco products, or alcohol at any time during clinical studies of ataluren.

If considered necessary for the patient's wellbeing, drugs for concomitant medical conditions or for symptom management may be given at the discretion of the investigator. The decision to authorize the use of any other drug(s) should take into account patient safety, the medical need, the potential for drug interactions, the possibility for masking symptoms of a more relevant underlying event, and whether use of a concomitant medication will compromise the outcome or integrity of the study.

Patients should be instructed about the importance of the need to inform the clinic staff of the use of any drugs or remedies (whether prescribed, over-the-counter, or illicit) before and during the course of the study. Information regarding any concomitant drugs taken by a patient during the course of the study and the reason for use will be recorded in the source documents and in the concomitant medication CRF.

6.5. Assistive Devices

During study-specified 6MWTs, timed function tests, North Star Ambulatory Assessments, and PUL assessments, patients must not use assistive devices.

6.6. Physical and Respiratory Therapy

There are neither restrictions nor prescriptions for physical or respiratory therapy during the study. Sites should use local best practices in providing physical therapy support for patients participating in the study. Respiratory care guidelines as suggested by the American Thoracic Society should be followed [ATS 2004]. Sites are encouraged to maintain the same general level of support throughout the duration of the study.

6.7. Dietary Restrictions

There are no specific dietary restrictions in the study.

7. SCHEDULE OF EVENTS AND STUDY PARAMETERS

7.1. Schedule of Events

The proposed types and timing of data to be recorded are described in [Table 3](#). Please see [Section 7.2](#) for cross-referenced explanations of the study procedures described in the tables.

Table 3. Schedule of Events

Study Period	Screening/ Baseline	Treatment Period											Post Treatment	
		Post-Treatment											144	6 Weeks Post-Tx
Study Week (±7 days)	Day 1	12	24	36	48	60	72	84	96	108	120	132	144	6 Weeks Post-Tx
Visit	1	2	3	4	5	6	7	8	9	10	11	12	13	14
Informed consent	X													
Vital signs	X ^a	X	X	X	X	X	X	X	X	X	X	X	X	X
Height	X ^a	X	X	X	X	X	X	X	X	X	X	X	X	X
Weight	X ^a	X	X	X	X	X	X	X	X	X	X	X	X	X
Physical examination	X ^a				X				X				X	
Hematology	X ^a	X	X	X	X	X	X	X	X	X	X	X	X	X
Biochemistry	X ^a	X	X	X	X	X	X	X	X	X	X	X	X	X
Urinalysis	X ^a	X	X	X	X	X	X	X	X	X	X	X	X	X
Renal ultrasound	X ^a				X				X				X	
12-lead ECG	X ^a				X				X				X	X
Study drug assignment	X													
Drug Dispensed	X	X	X	X	X	X	X	X	X	X	X	X		
Drug compliance		X	X	X	X	X	X	X	X	X	X	X	X	
Adverse events	X	X	X	X	X	X	X	X	X	X	X	X	X	X
Concomitant medication	X	X	X	X	X	X	X	X	X	X	X	X	X	X
6-minute walk test	X ^a	X	X	X	X	X	X	X	X	X	X	X	X	
Timed function tests	X ^a	X	X	X	X	X	X	X	X	X	X	X	X	
North Star Ambulatory Assessment	X ^a	X	X	X	X	X	X	X	X	X	X	X	X	
Activities of Daily Living/Disease Status Survey	X ^a	X	X	X	X	X	X	X	X	X	X	X	X	
PODCI Questionnaire	X ^a	X	X	X	X	X	X	X	X	X	X	X	X	
Spirometry	X		X		X		X		X		X		X	
PUL assessment	X	X	X	X	X	X	X	X	X	X	X	X	X	
Pharmacokinetics		X	X	X	X	X	X	X	X	X	X	X	X	

Study procedure need not be performed if Day 1 is within 14 days of the end-of-study evaluations at Week 48 (Visit 8) of the preceding Phase 3 double-blind study (PTC124-GD-020-DMD).

Abbreviations:; D/C = discontinuation; ECG = electrocardiogram; F/U = follow-up; PUL = Performance of Upper Limb, Tx = treatment

7.2. Explanation of Study Procedures

7.2.1. Transition from the Phase 3 Study, Ataluren Treatment, and Follow-up Periods

Every effort should be made to conduct the Screening/Baseline visit (Visit 1) on Day 2 of the End-of-Treatment visit (Visit 8/Week 48) of the Phase 3 double-blind study (PTC124-GD-020-DMD) to avoid interruption in treatment with study drug. Signature of the informed consent/assent document(s) for this study should be obtained after completion of the Day 2 study procedures at the End-of-Treatment visit (Visit 8/Week 48) of the Phase 3 double-blind study (PTC124-GD-020-DMD).

In this Phase 3 extension study, clinic visits have been simplified from 2-day to 1-day visits to reduce burden for the patients and study sites. For patients on an intermittent treatment regimen of a corticosteroid, clinic visits should be scheduled such that study-related evaluations are performed at the same approximate timepoint within a patient's corticosteroid regimen in order to avoid confounding effects due to the corticosteroids.

7.2.2. Screening/Baseline Visit (Visit 1)

Following signature of the informed consent/assent document(s), the patient will complete the necessary screening evaluations. It should be noted that results from safety laboratory tests from End-of-Treatment visit (Visit 8/Week 48) of the Phase 3 study (PTC124-GD-020-DMD) are not required to determine eligibility. Patients who have been confirmed to be eligible by the investigator for this extension study should complete all Screening/Baseline (Visit 1) study procedures. Most of the data collected during the End-of-Treatment visit (Visit 8/Week 48) of the Phase 3 study (PTC124-GD-020-DMD) can be utilized for the baseline assessments (see footnote "a" of [Table 3](#)). If the Baseline visit (Visit 1) is not completed within 14 days of the End-of-Treatment visit (Visit 8/Week 48) of the Phase 3 study (PTC124-GD-020-DMD), all study procedures should be performed.

After the completion of the baseline study procedures, a site representative should access the IVR/IWR system and supply the necessary information to obtain ataluren dosing instructions. The patient will remain at the clinic until ataluren supply for the next 12 weeks has been dispensed and the patient/caregiver has been instructed regarding ataluren storage, preparation, and administration.

7.2.3. Treatment Visits during Study (Visits 2 through 12)

Each patient will subsequently return to the clinical research facility during Week 12 (Visit 2), Week 24 (Visit 3), Week 36 (Visit 4), Week 48 (Visit 5), Week 60 (Visit 6), Week 72 (Visit 7), Week 84 (Visit 8), and Week 96 (Visit 9), Week 108 (Visit 10), Week 120 (Visit 11), and Week 132 (Visit 12). Because of potential changes in patient body weight over time, a site representative should enter the patient's current body weight into the IVR/IWR system at Week 24 (Visit 3), Week 48 (Visit 5), Week 72 (Visit 7), and Week 120 (Visit 11) to appropriately modify ataluren dosing instructions.

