6.1.4. Study Drug Dispensing

Dosing of ataluren will be based on milligrams of drug per kilogram of patient body weight at Screening/Baseline (Visit 1) and will be adjusted to allow for dosing with the available sachet dose strengths. The sachet dosage strengths and number of sachets to be taken per dose will be provided by the IVR/IWR system.

The clinic staff (eg, pharmacist or other qualified person) will be responsible for dispensing study drug according to the IVR/IWR system directions. Sufficient study drug will be provided for each study period at the beginning of the period.

Because of potential changes in patient body weight over time, weight-based dose adjustments will occur every 6 months. Depending upon the magnitude of change in patient body weight since baseline, the number and type of sachets to be used by the patient may remain the same or may be adjusted.

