7.5. Height, Weight, and Physical Examination

Standing height (in cm) will be measured at Screening/Baseline on Visit 1, Week 12 (Visit 2), Week 24 (Visit 3), Week 36 (Visit 4), Week 48 (Visit 5), Week 60 (Visit 6), Week 72 (Visit 7), Week 84 (Visit 8), Week 96 (Visit 9) Week 108 (Visit 10), Week 120 (Visit 11), Week 132 (Visit 12), Week 144 (Visit 13- End-of-Treatment/Premature Discontinuation), and at the Post-Treatment visit (6 weeks post discontinuation of study drug).

For nonambulatory patients, due to the difficulty in obtaining an accurate standing height measurement, ulna length and arm span will be used as a surrogate measure for height (see Study Manual). Ulna length and arm span (in cm) will be measured at Screening/Baseline on Visit 1, Week 12 (Visit 2), Week 24 (Visit 3), Week 36 (Visit 4), Week 48 (Visit 5), Week 60 (Visit 6), Week 72 (Visit 7), Week 84 (Visit 8), Week 96 (Visit 9) Week 108 (Visit 10), Week 120 (Visit

11), Week 132 (Visit 12), Week 144 (Visit 13 - End-of-Treatment/Premature Discontinuation), and at the Post-Treatment visit (6 weeks post discontinuation of study drug).

Weight (in kg) will be measured at Screening/Baseline on Visit 1, Week 12 (Visit 2), Week 24 (Visit 3), Week 36 (Visit 4), Week 48 (Visit 5), Week 60 (Visit 6), Week 72 (Visit 7), Week 84 (Visit 8), Week 96 (Visit 9) Week 108 (Visit 10), Week 120 (Visit 11), Week 132 (Visit 12), Week 144 (Visit 13- End-of-Treatment/Premature Discontinuation), and at the Post-Treatment visit (6 weeks post discontinuation of study drug).

A full physical examination (including evaluation of cardiovascular system, chest and lungs, thyroid, abdomen, nervous system, skin and mucosae, musculoskeletal system, eyes, ears, nose, mouth, throat, spine, lymph nodes, extremities, and genitourinary) will be conducted at Screening/Baseline (Visit 1), Week 48 (Visit 5), and Week 96 (Visit 9) and Week 144 (Visit 13 – End of Treatment/Premature Discontinuation) visit.

Physical exams may also be performed at any time during the study as clinically indicated.

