7.11. Study Drug Administration

Patients should take study drug TID as described in [Section 6.2.2](#) Study drug supply sufficient for each 12-week treatment period will be supplied to the patient at Screening/Baseline (Visit 1), Week 12 (Visit 2), Week 24 (Visit 3), Week 36 (Visit 4), Week 48 (Visit 5), Week 60 (Visit 6), Week 72 (Visit 7), and Week 84 (Visit 8) Week 96 (Visit 9) Week 108 (Visit 10), Week 120 (Visit 11), Week 132 and Week 132 (Visit 12). Sufficient drug for 90 days (12 weeks + 6 days) will be provided at each of these visits so lessen the likelihood that patients will experience drug shortages due to inadvertent loss of some of the sachets or scheduling delays for return visits.

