7.22. Blood for Analysis of Pharmacokinetics

Blood for trough ataluren concentrations will be collected at Week 12 (Visit 2), Week 24 (Visit 3), Week 36 (Visit 4), Week 48 (Visit 5), Week 60 (Visit 6), Week 72 (Visit 7), Week 84 (Visit 8), and Week 96 (Visit 9) Week 108 (Visit 10), Week 120 (Visit 11), Week 132 (Visit 12), Week 144 (Visit 13-End-of-Treatment/Premature Discontinuation immediately prior to the morning

dose of study drug. The Central Laboratory Manual should be consulted for collection, processing, and shipping details.

Samples will be stored at the bioanalytical lab for analysis of ataluren parent drug using a validated high performance liquid chromatography with tandem mass spectrometry (HPLC/MS-MS) method. Thereafter, samples will be retained at the bioanalytical lab for potential follow-up analyses of ataluren metabolites or corticosteroid parent drug and metabolites.

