13.1.6. Trough Ataluren Plasma Concentrations

Collection of plasma for ataluren concentrations is important for confirming maintenance of exposure over time. Having these data may allow correlations of exposure with measures of efficacy and toxicity. Because the ataluren PK profile has been well characterized in existing Phase 2a studies in patients with DMD, plasma sampling will be limited to before dosing relative to the morning dose at each clinic visit. This will provide information regarding ataluren trough concentrations. The high performance liquid chromatography with tandem mass spectrometry (HPLC/MS-MS) method that will be used to quantify ataluren plasma concentrations has been fully validated in the context of the prior Phase 1 and Phase 2 studies. Plasma samples will be retained for potential later analyses of ataluren metabolites or corticosteroid parent drug and metabolites.

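### Protocol Section 7.2.3 leaves Week 96 out of the weight-entry visits, so the dose can go 48 weeks without a weight update although Section 6.1.4 requires one every six months

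*Protocol*

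**What the plan says.** Protocol Section 6.1.4 bases the first dose on the Screening/Baseline weight and then gives a general rule, "weight-based dose adjustments will occur every 6 months", because body weight may change. It also says that the "number of sachets to be taken per dose will be provided by the IVR/IWR system", and that after a weight update the sachets "may remain the same or may be adjusted".

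Protocol Section 7.2.3 gives the same reason and turns the rule into visits. Current weight is to be entered in the IVR/IWR system on this schedule: "Week 24 (Visit 3), Week 48 (Visit 5), Week 72 (Visit 7), and Week 120 (Visit 11) to appropriately modify ataluren dosing instructions". The sentence just before it names Week 96 (Visit 9) as a scheduled treatment visit.

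Other sections show what happens at that visit. Section 7.5 opens its weight schedule with "Weight (in kg) will be measured at Screening/Baseline on Visit 1" and continues through every clinic visit, Week 96 included. Section 7.11 includes it among the dispensing visits: "Week 84 (Visit 8) Week 96 (Visit 9) Week 108 (Visit 10". Section 7.22 sets the trough schedule: "Blood for trough ataluren concentrations will be collected at Week 12 (Visit 2" and every 12 weeks after that to Week 144, before the morning dose. Section 13.1.6 calls these samples "important for confirming maintenance of exposure over time".

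**The concern.** The two dosing instructions cannot both be met by a site that works from the visit list alone. The list keeps a 24-week rhythm up to Week 72, skips one step, and resumes at Week 120. No reason is given for a longer interval at that stage.

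Measuring weight at Week 96 does not change the dose by itself, because the sachets are set by the IVR/IWR system from the weight entered. A growing boy whose weight is not entered at Week 96 would receive less than the intended mg/kg until Week 120. Long-term plasma exposure is a secondary objective, and SAP Section 5.8.12 summarizes troughs by visit. A lower mean at Weeks 108 and 120 could then partly reflect a missed dose update rather than a change in how the drug is handled. The exposure summary in SAP Section 5.6 covers compliance and treatment duration, not mg/kg received, so it would not reveal the cause.

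**Working it through.** **Intervals**

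Inputs: baseline weight at Week 0 (Section 6.1.4); entries at Weeks 24, 48, 72 and 120 (Section 7.2.3); treatment to Week 144 (Section 6.2.1). Months = weeks × 7 / 30.4375.

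| Schedule | Weeks | Intervals (weeks) | Intervals (months) |
|---|---|---|---|
| As listed | 0, 24, 48, 72, 120, end 144 | 24, 24, 24, 48, 24 | 5.5, 5.5, 5.5, 11.0, 5.5 |
| With Week 96 added | 0, 24, 48, 72, 96, 120, end 144 | 24 throughout | 5.5 throughout |

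The six-monthly rule is reproduced at every step except Week 72 to Week 120. Adding Week 96 restores it.

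**What the gap covers**

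- Treatment time: Weeks 96 to 120 = 24 of 144 weeks = 16.7%.
- Trough visits: every 12 weeks from Week 12 to Week 144 = 12 visits.
- The Week 96 trough is drawn before that morning's dose, on supply dispensed at Week 84. It rests on the Week 72 weight under either schedule and is not affected.
- The Week 108 and Week 120 troughs follow supply dispensed at Weeks 96 and 108. These two are affected.

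**Illustration of size**

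The documents give neither patient weights over time nor a sachet-rounding rule, so these inputs are assumptions: W = 30 kg at Week 72, with a linear gain of g = 2 to 6 kg over the next 48 weeks. The daily dose is 10 + 10 + 20 = 40 mg/kg.

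- Dose on the Week 72 weight: 40 × 30 = 1200 mg/day.
- Dose on the Week 96 weight: 40 × (30 + g/2) = 1240 mg/day (g = 2) or 1320 mg/day (g = 6).
- Extra shortfall = (g/2) / (W + g/2) = 1/31 = 3.2% (g = 2) or 3/33 = 9.1% (g = 6). With g = 0 it is 0.

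| Visit | g (kg) | Weight (kg) | Week 96 skipped (mg/kg/day) | Week 96 entered (mg/kg/day) |
|---|---|---|---|---|
| Week 108 | 2 | 31.5 | 1200/31.5 = 38.1 | 1240/31.5 = 39.4 |
| Week 108 | 6 | 34.5 | 1200/34.5 = 34.8 | 1320/34.5 = 38.3 |
| Week 120 | 2 | 32 | 1200/32 = 37.5 | 1240/32 = 38.75 |
| Week 120 | 6 | 36 | 1200/36 = 33.3 | 1320/36 = 36.7 |

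All of these are before rounding to sachets.

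**The case against.** The strongest reply is that Section 6.1.4 already gives the right answer. Section 7.2.3 says that weight should be entered at the listed visits; it does not forbid entry at others. A site or an IVR/IWR build that follows the six-monthly rule would update at Week 96 without breaching either section. The documents do not show whether the system prompts for weight at that visit, so no dosing effect is demonstrated. This stands, and it makes the 24 weeks and 2 trough visits upper limits. It does not remove the conflict, because the section with the operational detail is the one that is wrong.

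The omission also looks like a drafting remnant rather than a decision. Section 7.23 still mentions a 96-week treatment period, and Section 13.1.7 still counts 8 post-baseline evaluations, which fits 96/12 = 8 and not 144/12 = 12. In a 96-week study, Week 96 would be the end of treatment and would need no weight entry. That is a plausible inference, and it supports correcting the list.

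Sachet rounding matters too. Strengths are 125, 250 and 1000 mg. In the illustration the per-dose differences are 10 to 30 mg (morning and mid-day) and 20 to 60 mg (evening), all below one 125 mg sachet. The real effect is therefore stepwise: none for some boys, a whole sachet for others. The smooth percentages give scale only.

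Finally, the SAP plans no test on troughs, and SAP Section 5.2 records the sponsor's decision to discontinue the study. Both points limit the consequence and the value of a prospective amendment.

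**Conclusion.** The inconsistency is real, and Section 7.2.3 is wrong as written. It allows 48 weeks between weight updates where Section 6.1.4 requires about 24. The SAP, which takes precedence over the protocol where they conflict, contains no weight-entry schedule and does not resolve it.

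The severity is minor. Confidence is high that the two sections conflict and low on the actual dosing effect, because that depends on the IVR/IWR prompts, the boys' weight gain and the rounding rule, none of which the documents give. The 3.2% to 9.1% range rests entirely on the assumed 30 kg weight and linear gain of 2 to 6 kg.

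**What to change.** Add Week 96 (Visit 9) to the weight-entry list in Section 7.2.3, and confirm that the IVR/IWR specification asks for weight at that visit. For boys already treated beyond Week 96, compare the recorded weights with the IVR/IWR dose assignments to see whether the update was made, and take any missed update into account when reading the Week 108 and Week 120 troughs.

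The cost is one phrase in the protocol and one system check. Weight is already collected at Week 96, so no new data are needed. With the study being discontinued, the check of past assignments is the more useful part.
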